- Independence of residuals (Durbin-Watson test)

- Absence of multicollinearity (Variance Inflation Factor < 5)
- Normality of residuals (Shapiro-Wilk on residuals)

Reported: Adjusted MD (β coefficient) with 95% CI, R^2 , adjusted R^2 , F-statistic, overall model p-value

SAP-4.3 CSD Prevalence — Analysis

Unadjusted:

- Chi-square test or Fisher's exact test (if expected cell count < 5)
- Relative Risk (RR) with 95% CI
- Absolute Risk Reduction (ARR) and Number Needed to Treat/Harm (NNT/NNH)

Adjusted:

- **Binary logistic regression** at 6–8 weeks and at 6–7 months
- Covariates: same set as RMT regression model
- Variables with $p < 0.20$ in univariate analysis AND a priori confounders (age, parity, BMI, indication) included
- Model fit: **Hosmer-Lemeshow test**
- Multicollinearity: **Variance Inflation Factors (VIF)**
- Discrimination: **Area Under the ROC Curve (AUC)**
- Results expressed as adjusted **Odds Ratios (OR)** with 95% CI

SAP-5. SECONDARY OUTCOME ANALYSES

SAP-5.1 Continuous Secondary Outcomes

- Unadjusted: t-test or Mann-Whitney U as appropriate
- Adjusted: Multiple linear regression (same covariate set)
- Results: Mean difference or median difference with 95% CI

SAP-5.2 Binary Secondary Outcomes (Complications, Transfusion)

- Unadjusted: Chi-square or Fisher's exact test
- Results: RR, ARR, NNT/NNH with 95% CI

SAP-5.3 CSD Morphological Dimensions

Analyzed within the **CSD-positive subgroup only**:

- Depth, length, width: Mann-Whitney U test
- **CSD Volume** (ellipsoid formula): Mann-Whitney U test

SAP-5.4 Repeated Measures — RMT at 6 Weeks and 6 Months

Method: Linear Mixed-Effects Model (LME)

Model structure:

- Fixed effects: treatment group, time point (6 weeks vs. 6 months), treatment × time interaction
- Random effect: participant-level intercept (accounts for within-subject correlation)
- Covariance structure: Unstructured (preferred); compound symmetry if convergence issues

Interpretation:

- Significant interaction ($p < 0.05$): treatment effect differs across time points
- Non-significant interaction: main effects interpreted independently

SAP-5.5 Symptom Outcomes (Ordinal / Binary)

- Binary symptoms (spotting, dyspareunia): Chi-square or Fisher's exact test; RR with 95% CI
- **Paired temporal evolution** (6 weeks → 6 months within each group): **McNemar's test**
- Adjusted: Binary logistic regression

SAP-5.6 Hemoglobin Variation and Blood Loss

- ΔHb : t-test or Mann-Whitney U; mean difference with 95% CI

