3.2 Secondary Objectives

1. To compare **intraoperative parameters** between groups, including hysterorrhaphy duration, total operative time, visually estimated blood loss (PSTEV), calculated total blood loss (PSTC), number of additional hemostatic sutures, and intraoperative complications.
2. To assess **immediate postoperative outcomes**, including hemoglobin variation (ΔHb), transfusion requirement, early postoperative complications (endometritis, wound infection, parietal hematoma, thromboembolic events, surgical revision), and hospital length of stay.
3. To evaluate **medium-term gynecological symptoms** potentially attributable to CSD at 6 weeks and 6 months, including postmenstrual spotting, prolonged menstruation (> 7 days), dysmenorrhea, chronic pelvic pain, menometrorrhagia, and dyspareunia.
4. To compare **CSD morphological characteristics** between groups, including defect depth, length, width, and estimated volume using the ellipsoid formula.
5. To assess the **adjacent myometrial thickness (AMT)** and the **myometrial ratio ($\text{RM} = \text{RMT}/\text{AMT} \times 100$)** at both evaluation time points.
6. To identify **clinical and surgical predictors** of CSD formation and reduced RMT.
7. To evaluate the **mediating role** of CSD at 6 weeks on RMT at 6 months.

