9.2 Secondary Outcomes

Ultrasonographic outcomes:

- CSD morphological dimensions: depth, length, width (mm)
- CSD volume: estimated by ellipsoid formula — $V \text{ (mm}^3\text{)} = (\pi/6) \times \text{Length} \times \text{Width} \times \text{Depth}$
- **Adjacent Myometrial Thickness (AMT)**: measured 5–10 mm from the scar on both sides (mm)
- **Myometrial Ratio (RM)**: calculated as $\text{RM (\%)} = \text{RMT} / \text{AMT} \times 100$
- Uterine position (anteverted / retroverted)

Intraoperative outcomes:

- **Hysterorrhaphy duration** (minutes and seconds)
- **Total operative time** (minutes and seconds)
- **Visually Estimated Blood Loss (PSTEV)**: volume of bloody fluid in suction canister at end of surgery, minus estimated amniotic fluid volume (mL)
- **Calculated Total Blood Loss (PSTC)**:

$$PSTC(mL) = \frac{VST \times (Hct_{preop} - Hct_{postop})}{35} \times 100 + \text{Compensated losses}$$

Where: VST (Total Blood Volume) = Pre-pregnancy weight (kg) \times 65 \times 1.4;
Compensated losses = Number of packed red blood cell units transfused \times 500 mL; 35 = reference hematocrit of one packed RBC unit

- Number of **additional hemostatic sutures**
- **Intraoperative complications**: hysterotomy extension, ureteral injury, bladder injury, intestinal injury, hemorrhage requiring transfusion

Immediate postoperative outcomes:

- **Hemoglobin variation**: $\Delta\text{Hb (g/dL)} = \text{Hb preoperative} - \text{Hb at Day 1 postpartum}$
- **Transfusion requirement** (packed RBC units)
- **Early postoperative complications**: postpartum endometritis, surgical site infection, parietal hematoma, surgical revision, thromboembolic events

- **Hospital length of stay (days)**

Medium-term symptom outcomes (at 6–8 weeks and 6–7 months):

- Postmenstrual spotting (characteristic of CSD)
- Prolonged menstruation (> 7 days)
- Dysmenorrhea requiring medication
- Chronic pelvic pain (outside menstruation)
- Menometrorrhagia
- Dyspareunia

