7.4 Paired Temporal Symptom Evolution

McNemar's test (within-group: 6 weeks \rightarrow 6 months)

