12. MISSING DATA

Little's MCAR test to assess missing data mechanism.

Outcome	Strategy
RMT at 6 months	Five-scenario MICE (SA-3)
Secondary continuous	Complete case + MICE if > 10% missing
Binary outcomes	Complete case
Symptom questionnaires	Full information maximum likelihood (FIML) via mixed models

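### The within-arm McNemar test on menses-dependent symptoms has no menstruating denominator and no code for women without periods, so return of periods could be reported as symptom worsening

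*SAP*

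**What the plan says.** Secondary objective 3 (combined document, section 3.2) covers complaints described as "potentially attributable to CSD at 6 weeks and 6 months, including postmenstrual spotting, prolonged menstruation (> 7 days), dysmenorrhea, chronic pelvic pain, menometrorrhagia, and dyspareunia". Section 9.2 lists the same six under "Medium-term symptom outcomes (at 6–8 weeks and 6–7 months", with wording such as "Prolonged menstruation (> 7 days" and "Dysmenorrhea requiring medication".

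For binary symptoms, SAP-5.5 plans chi-square or Fisher's exact tests with RR between arms, adjusted logistic regression, and McNemar's test for the paired change ("6 weeks → 6 months within each group"). It names only spotting and dyspareunia as examples. Section 7.4 of the combined document has the same paired test, "McNemar's test (within-group: 6 weeks" to 6 months, for symptoms generally.

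On missing data, SAP-10 and section 12 of the combined document each have a complete-case row for binary outcomes and a separate row for symptom questionnaires. In section 12 that row reads "Full information maximum likelihood (FIML) via mixed models".

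Neither document makes return of menses an analysis variable, a denominator or a response code. The menstrual cycle at follow-up appears only as a timing preference for the ultrasound (section 10).

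**The concern.** Spotting after a period, or a period longer than seven days, cannot occur before a period has. Dysmenorrhea also needs menses, and menometrorrhagia does so less strictly. Chronic pelvic pain does not. Dyspareunia has a parallel gap, because it needs resumed intercourse.

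At 6–8 weeks after birth some women will have had no period. Recorded as 'no', they enter McNemar's test as symptom-free at the first visit. Those whose periods return by 6–7 months can then only stay symptom-free or appear to worsen. The paired test would mix symptom change with resumption of periods, in both arms alike, and could not be read as evidence about symptoms attributable to the scar.

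The SAP already handles this kind of problem elsewhere: SAP-5.3 restricts the CSD dimensions to CSD-positive women. The menses-dependent symptoms have no such rule.

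**Working it through.** **Plan figures.** The plan gives no power or expected rate for symptoms, so there is no figure of that kind to reproduce. Its RMT sample size does reproduce: 2 × (1.96 + 0.842)² × 3.5² / 1.3² = 113.8, so 114 per group, and 114 / 0.70 ≈ 163. For pairs per arm I use the enrolled number less the anticipated loss (section 11): 192 × 0.70 = 134.4, so 134. Alpha is 0.05, two-sided.

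**Assumptions, none of them in the documents.** Shares m1 and m2 of women menstruate at the two visits. The symptom risk r among menstruating women is the same at both visits, so there is no true change. Women menstruating at the first visit still are at the second. Women without menses are coded 'no'.

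**Discordant pairs.** Let b be the probability of no→yes and c of yes→no.
- Symptom a fixed trait: b = (m2 − m1)r, c = 0.
- Symptom independent between visits: b = (m2 − m1)r + m1·r(1 − r), c = m1·r(1 − r).

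**Worked case: m1 = 25%, m2 = 70%, r = 20%.** All-women prevalence moves from 0.25 × 0.20 = 5% to 0.70 × 0.20 = 14%.
- Fixed trait: b = 0.45 × 0.20 = 0.09, or 12.1 pairs, against none. With c = 0, six one-way pairs already give p = 2 × 0.5⁶ = 0.031. Exact McNemar is significant in about 98% of arms.
- Independent: b = 0.09 + 0.25 × 0.20 × 0.80 = 0.13, or 17.4 pairs, against c = 0.04, or 5.4 pairs. It is significant in about 66% of arms.

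**Holm.** The documents do not define the Holm family. Taking six symptoms in two arms as the family (an assumption), the first-step threshold is 0.05/12, and the rates become about 86% (fixed trait) and 30% (independent).

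**Low end: m1 = 40%, m2 = 50%, r = 10%.** Fixed trait: 134 × 0.01 = 1.3 pairs, significant in about 0.3% of arms. Independent: 6.2 against 4.8 pairs, about 3.4%. Both are below the nominal 5%.

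**Intermediate correlation** (half of the symptom states carry over; 4,000 replicates, 134 pairs). Chance of a significant worsening:

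| Menses share | r = 10% | r = 20% | r = 30% |
|---|---|---|---|
| 20% → 80% | 66% | 96% | >99% |
| 40% → 80% | 27% | 64% | 85% |
| 60% → 80% | 7% | 17% | 28% |
| 80% → 90% | 3% | 6% | 8% |
| 80% → 80% | about 1% | about 1% | about 1% |

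With McNemar limited to women menstruating at both visits, total two-sided rejection is at most about 3% in every row.

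**Between arms at 6–8 weeks.** Take true risks of 30% and 15% among menstruating women and an equal menses share m in both arms. At m = 30% the all-women risks are 9% and 4.5%. The RR is 2 either way (30/15 and 9/4.5), while the ARR falls from 15 to 4.5 points. Power with 134 per arm is Φ[(Δ − 1.96·SE₀)/SE₁], with SE₀ from the pooled risk and SE₁ from the two separate risks. At m = 40%, Δ = 0.12 − 0.06 = 0.06, SE₀ = √(2 × 0.09 × 0.91/134) = 0.0350 and SE₁ = √((0.12 × 0.88 + 0.06 × 0.94)/134) = 0.0348, giving 40%. It is 84% if all menstruate, 58% at m = 60% and 22% at m = 20%.

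**Missing-data rows.** Coded 'no', the woman stays in and the artifact arises. Left blank, the complete-case row drops her pair and the artifact disappears. Under the mixed-model row she is treated as having an unobserved value, although none exists. SAP-5.5 lists no mixed model for symptoms, so the two rows are not tied to the planned tests.

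**The case against.** A reader might infer that the plan will report resumed periods as worsening. The documents do not support that. It needs 'no' coding and a clear rise in the share menstruating; the first is not specified and the second not given. Complete-case handling of blank items would remove the artifact, and a small rise makes it slight.

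A reader might also infer that the randomized comparison at 6–8 weeks is biased. It is not, if menses return equally in both arms: the RR that SAP-5.5 reports is unchanged, and only power is lost. ARR and NNT are planned in SAP-5.2 for complications and transfusion. They could reach symptoms only through the general binary-outcome rule in section 7.3 of the combined document. The comparison between arms at 6–7 months is already planned and addresses objective 3.

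Nor can one say that menses status is not collected. Section 10 cites a standardized questionnaire whose content is not shown. What is missing is an analysis rule.

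These are secondary, exploratory outcomes under Holm correction, and no primary endpoint is touched. All of this stands, and it limits the point to unspecified coding and denominator. It does not supply the missing rule. The SAP says it is meant to avoid post-hoc analytical decisions, and this decision is still open.

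**Conclusion.** The concern holds in a limited form. Both documents plan a within-arm paired test that covers menses-dependent symptoms, without saying who is in the denominator or how a woman without periods is coded. With 'no' coding, resumption of periods could appear as worsening in both arms.

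The size cannot be fixed from the documents. Over the assumed inputs the false-significance rate runs from under 1% to nearly 100%, so the worked case of 66–98% illustrates the risk and does not estimate it. Holm correction is only a partial protection. Between arms, the consequence at 6–8 weeks is lost power and a diluted ARR, given equal return of menses. The point should be settled before database lock, but it does not affect the primary conclusions.

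**What to change.** Amend SAP-5.5 and SAP-10, and sections 7.4 and 12 of the combined document, as follows.

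1. Code a woman without menses since delivery as 'not applicable' for the menses-dependent symptoms, and a woman who has not resumed intercourse as 'not applicable' for dyspareunia. Such answers are neither 'no' nor missing values to be modelled by FIML. State whether menometrorrhagia follows this rule.
2. Limit McNemar's test for these symptoms to women menstruating at both visits, or drop it for them.
3. Report the proportion menstruating per arm at each visit, and show between-arm results among menstruating women beside the all-women results.
4. Reconcile the complete-case row for binary outcomes with the mixed-model row for symptom questionnaires, so that each symptom analysis has one rule.

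Use the menses status already recorded, or obtain it at visits still to come where possible. Recruitment ran through 2025 and the SAP is dated April 2026, so new collection is too late for most women. If status is unavailable, dropping McNemar for these symptoms is the simpler choice.

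The cost is mainly SAP wording. The downsides are fewer pairs and conditioning on a post-randomization status; the proportion menstruating per arm is the check on the latter.

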Type of cesarean section	Scheduled vs. Intrapartum	Interaction term
Surgeon category	Senior vs. Resident Year 4–5	Interaction term

Test for interaction: Likelihood ratio test comparing models with and without the interaction term.

All subgroup analyses are exploratory and hypothesis-generating. No correction for multiple comparisons is applied to subgroup analyses; results will not drive primary conclusions.

Results will be presented in **forest plots**.

SAP-8. SENSITIVITY ANALYSES

Analysis	Method
SA-1: Per-Protocol population	Repeat primary analysis in PP population
SA-2: Intraoperative complication exclusion	Exclude participants with major intraoperative events (corporeal hysterotomy, hysterotomy extension > 2 cm)
SA-3: Multiple imputation for missing RMT	MICE — 5 scenarios: observed data, LOCF, best case, worst case, 6-week status carry-forward
SA-4: Inverse Probability Weighting (IPW)	Adjust for informative loss to follow-up
SA-5: Binary threshold analysis	Proportion with RMT < 2.5 mm and RMT < 3.0 mm; Chi-square test
SA-6: Complete case analysis	For comparison with imputed results

SAP-9. MULTIPLICITY AND TYPE I ERROR CONTROL

- **Primary outcomes:** $\alpha = 0.05$, two-sided, for each co-primary endpoint (RMT and CSD prevalence at 6 weeks and 6 months)
- **Secondary outcomes:** Exploratory; **Holm-Bonferroni correction** applied to control family-wise error rate
- **Unmeasured confounders:** **E-value** calculated to quantify the minimum strength of an unmeasured confounder needed to explain away observed associations

SAP-10. MISSING DATA STRATEGY

Data Type	Strategy
Primary outcome (RMT at 6 months)	Five imputation scenarios (MICE)
Secondary continuous outcomes	Complete case + sensitivity with imputation if > 10% missing
Binary outcomes	Complete case analysis

Symptom questionnaires	Linear mixed model (full information maximum likelihood)
------------------------	--

Missing data mechanism assessed by **Little's MCAR test**.

Participants lost to follow-up compared to completers on key baseline variables; reasons for dropout documented and reported.

SAP-11. PRESENTATION OF RESULTS

Results reported in accordance with **CONSORT 2010** guidelines:

- **Table 1:** Baseline characteristics (ITT population) — no p-values
- **Figure 1:** CONSORT flow diagram
- **Table 2:** Primary and secondary outcomes with between-group comparisons
- **Table 3:** Subgroup analysis (forest plots)
- **Table 4:** Multivariate analysis results

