11. SAMPLE SIZE CALCULATION

The sample size was determined based on the primary outcome — **RMT at 6 months** — using the standard formula for comparison of two independent means:

$$n = \frac{2 \times (Z_{\alpha/2} + Z_{\beta})^2 \times \sigma^2}{\Delta^2}$$

Parameters:

- Two-sided significance level: $\alpha = 0.05$ ($Z_{\alpha/2} = 1.96$)
- Statistical power: 80% ($Z_{\beta} = 0.842$)
- Conservative standard deviation: **$\sigma = 3.5$ mm**
- Minimum clinically meaningful difference: **$\Delta = 1.3$ mm**

Base sample size: 114 participants per group

Adjustment for loss to follow-up:

Based on local postpartum follow-up data and published literature, a **30% loss to follow-up rate** was anticipated:

$$n_{adjusted} = \frac{114}{1 - 0.30} \approx 163 \text{ per group}$$

Total enrolled: 384 participants (192 per group)

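### Symptom change from 6 weeks to 6 months is tested only inside each arm; no between-arm contrast of change is written down

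*SAP*

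**What the plan says.** Secondary objective 3 (combined document, section 3.2) is to evaluate symptoms "potentially attributable to CSD at 6 weeks and 6 months, including postmenstrual spotting, prolonged menstruation (> 7 days), dysmenorrhea" and three others, six in all.

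SAP-5.5 plans a between-arm comparison of status: "Binary symptoms (spotting, dyspareunia): Chi-square or Fisher's exact test; RR with 95% CI", with adjusted logistic regression as well. Section 7.3 of the combined document gives the same type of test for binary outcomes.

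For change over time, SAP-5.5 specifies McNemar's test, "6 weeks → 6 months within each group". Section 7.4 of the combined document repeats it: "McNemar's test (within-group: 6 weeks" to 6 months.

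For RMT the plan goes further. SAP-5.4 lists "Fixed effects: treatment group, time point (6 weeks vs. 6 months), treatment × time interaction". Section 7.1 gives the same terms without naming an outcome; symptoms have their own entry in section 7.4.

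The missing-data tables also assign symptom questionnaires a longitudinal model: "Linear mixed model (full information maximum likelihood" in SAP-10 and "Full information maximum likelihood (FIML) via mixed models" in section 12. Neither entry states fixed effects, an interaction or a contrast.

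**The concern.** A McNemar test inside one arm asks whether that arm changed. The answer mixes the natural postpartum course with any effect of technique and makes no use of the randomization. Two such p-values, one below 0.05 and one above, are not evidence that the arms differ. The quantity that compares the techniques is the difference in change, and the plan writes no test or interval for it.

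At stake is how the symptom results are read. A report with a significant improvement after one closure and a non-significant one after the other is easily taken to mean that symptoms resolve after only one technique. The plan already uses the right tool for RMT and for the subgroup analyses, where it specifies interaction terms, so symptom change departs from its own practice.

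**Working it through.** **Inputs from the documents.** 192 women per arm and 30% anticipated loss (combined document, section 11); two-sided α = 0.05 (stated there for the sample size, assumed here for McNemar); Holm-Bonferroni for secondary outcomes (SAP-9, section 11 of the combined document's SAP).

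**The plan's own figure.** The only power calculation is for RMT: 2 × (1.96 + 0.842)² × 3.5² / 1.3² = 113.8, so 114 per group, and 114 / 0.70 = 163. Both reproduce. No figure is given for symptoms or symptom change.

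**Pairs per arm.** 192 × 0.70 = 134.4, taken as 134.

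**Formula.** Two independent arms with the same true course have the same within-arm power p. Then P(exactly one arm significant) = p(1−p) + (1−p)p = 2p(1−p). Examples: p = 0.05 gives 9.5%; 0.20 gives 32%; 0.50 gives 50%, the maximum; 0.80 gives 32%; 0.90 gives 18%.

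**Exact McNemar with 134 pairs per arm.** Symptom rates are assumed and identical in both arms; the within-woman latent correlation is 0.3 or 0.6, and ranges span the two values. The last column uses 0.05/12 = 0.0042, the strictest Holm step if the family were only six symptoms × two arms.

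| True rate, 6 weeks → 6 months | Power per arm, α = 0.05 | One arm only, α = 0.05 | One arm only, α = 0.05/12 |
|---|---|---|---|
| 20% → 20% (no change) | 3% | 6% | 0.5% |
| 10% → 8% | 6–7% | 11–12% | 1% |
| 20% → 17% | 8% | 14–15% | 2% |
| 20% → 12% | 41–51% | 48–50% | 23–30% |
| 25% → 15% | 54–65% | 45–50% | 33–42% |
| 30% → 20% | 49–59% | 48–50% | 28–38% |
| 10% → 20% | 63–74% | 38–47% | 40–47% |
| 30% → 10% | 99% or more | 0.2–1.4% | 3–12% |

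Holm lowers the rate in most rows. It can raise it where uncorrected power is high, as in the last row. The ceiling of 50% does not depend on α; a stricter α only moves it to a larger change.

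**Direct comparison.** In 200,000 simulated trials per scenario with identical arms and 134 pairs each, a Wald test on the between-arm difference in paired change was set against the two exact McNemar tests. Discordant rates are the proportions of women changing in each direction.

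| Discordant rates | One arm only (two McNemar tests) | Between-arm test rejects |
|---|---|---|
| 10% and 10% | 5.8% | 5.1% |
| 15% and 7% | 48.9% | 5.1% |
| 20% and 8% | 41.1% | 5.2% |

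The direct test stays close to its nominal 5% whatever the common course.

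**The case against.** The strongest reply is that the randomized symptom comparison is already planned. Symptoms are first recorded at 6–8 weeks, after surgery, so there is no pre-treatment baseline. The effect of technique on symptoms is the arm contrast at each visit, and SAP-5.5 and section 7.3 provide for between-arm tests. On this view, change between two postoperative visits is a supplementary description. That stands, and it limits the point to change.

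Second, a reader might infer that objective 3 requires a comparison of symptom course. It does not say so. It speaks of evaluating symptoms at two time points, and the aim of assessing stability over time is stated only for RMT and CSD in section 3.1.

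Third, a reader might infer that the plan intends to conclude a technique difference from the two McNemar results. Neither SAP-5.5 nor section 7.4 says so. The risk lies in how the results may be read.

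Fourth, a mixed model is named for symptoms, so McNemar is not the only longitudinal method mentioned. True, but a model without terms tests nothing in particular, and a linear model does not match the binary treatment in SAP-5.5. This makes the repair easier; it does not make it unnecessary.

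Finally, the rate near one half depends on assumed rates that put power near 50%, and on uncorrected α. Both are correct, and the table shows how far the rate falls elsewhere.

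**Conclusion.** The gap is real but modest. The plan tests symptom change only within arms and pre-specifies no between-arm contrast of it. With identical true courses, one-arm-only significance occurs with probability 2p(1−p): about 6% with no true change, 11–15% for the changes of 2–3 percentage points examined, and at most 50%. The documents do not support reading the 50% as the expected rate. It is a ceiling, reached only when within-arm power is near one half, and it falls to about 1% or less for a change as large as 30% to 10% at α = 0.05. Nor do they support saying that symptoms go uncompared between arms.

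These figures rest on 134 pairs per arm, exact McNemar tests and assumed symptom rates and correlations. SAP-9 labels secondary outcomes exploratory, and the primary conclusion and the planned symptom-status comparisons are unaffected. The change is worth making because it is cheap and closes an open specification at the same time.

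**What to change.** In SAP-5.5 and section 7.4, and as the symptom model named in SAP-10 and section 12, specify for each binary symptom a logistic mixed model or a binomial GEE with arm, visit and arm × visit. Report the arm contrast at each visit and the between-arm difference in change, each with a 95% CI, and state the scale of that difference (ratio of odds ratios, or difference in risk change). Replace the linear label in SAP-10.

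Present within-arm percentages at each visit descriptively. If McNemar's test is kept, label it descriptive and add a sentence that within-arm results are not used to infer a difference between techniques.

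The cost is SAP wording and one additional standard model per symptom, in R, which the plan already uses for mixed models. No new data are needed. The downside is low precision for the interaction when a symptom is rare; the confidence interval will show this.

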All randomized participants who underwent the surgical intervention (regardless of which technique was ultimately performed).

Protocol deviations will be prospectively classified as **major** (potentially affecting primary outcome validity) or **minor** (unlikely to affect outcomes) and documented in a deviation log.

SAP-3. BASELINE CHARACTERISTICS

Baseline characteristics will be summarized for the **ITT population** by treatment group:

Variable Type	Summary Statistic
Continuous, normally distributed	Mean ± Standard Deviation
Continuous, non-normal distribution	Median (Interquartile Range, IQR)
Categorical	n (%)

Normality of continuous variables will be assessed using both the **Kolmogorov-Smirnov test** and the **Shapiro-Wilk test**, complemented by visual inspection of Q-Q plots and histograms.

Variables to be summarized include: age, BMI at delivery, gestational age, parity, indication for cesarean section, type of anesthesia, skin incision type, uterine exteriorization status, pre-operative hemoglobin and hematocrit, and attending surgeon (anonymized).

No inferential statistics (p-values) will be calculated for baseline comparisons, as any imbalances in a randomized trial result from chance rather than systematic bias (CONSORT Statement 2010).

SAP-4. PRIMARY OUTCOME ANALYSIS

Outcomes:

1. **RMT** at 6–8 weeks and 6–7 months (continuous, mm)
2. **CSD prevalence** at 6–8 weeks and 6–7 months (binary)

SAP-4.1 RMT — Unadjusted Analysis

- **If normally distributed:** Independent samples **t-test** (or Welch's t-test if unequal variances)
- **If non-normally distributed: Mann-Whitney U test**

Reported statistics:

- Mean \pm SD (or Median [IQR]) per group
- Mean difference (MD) with 95% Confidence Interval
- Two-sided p-value (significance threshold: $\alpha = 0.05$)
- Effect size: Cohen's d (t-test) or rank-biserial correlation (Mann-Whitney)

SAP-4.2 RMT — Adjusted Analysis (Primary)

A **multiple linear regression model** will be constructed:

Dependent variable: RMT at 6–7 months

Independent variables:

- Treatment group (primary predictor)
- Age (continuous)
- BMI (continuous)
- Gestational age (continuous)
- Uterine exteriorization (yes/no)
- Surgeon experience level (senior/resident Year 4–5)
- Duration of labor before cesarean section (if applicable)
- Indication for cesarean section

Model assumptions verified:

- Linearity (partial regression plots)
- Homoscedasticity (Breusch-Pagan test)

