10. DATA COLLECTION AND FOLLOW-UP SCHEDULE

Time Point	Assessment
Preoperative	Eligibility verification, informed consent, baseline NFS (CBC), demographics
Intraoperative	Randomization, surgical parameters, hysterorrhaphy duration, operative time, blood loss, complications
Postoperative Day 1	NFS (hemoglobin), vital signs, wound assessment
Discharge	Wound assessment, clinical evaluation, length of stay
6–8 Weeks postpartum	TVUS (RMT, CSD assessment), AMT, RM, clinical examination, standardized symptom questionnaire
6–7 Months postpartum	TVUS (RMT, CSD — PRIMARY ENDPOINT) , AMT, RM, CSD dimensions, volume, standardized symptom questionnaire

Ultrasonographic Examination Protocol

All TVUS examinations are performed:

- By a **dedicated, trained ultrasonographer per center, blinded to group allocation**
- Using **Samsung HS40 ultrasound system with EVN4-9 endovaginal probe (4–9 MHz)**
- With **standardized imaging parameters**

- With the **bladder empty**
- **Preferably in the follicular phase (Day 7–14 of the menstrual cycle)** to optimize defect visualization
- In the **mid-sagittal plane**: depth, length, and RMT measured; width measured in transverse plane
- **RMT measured perpendicular to the serosa at the thinnest point of the scar**

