6. PRIMARY OUTCOME STATISTICAL ANALYSIS

6.1 RMT Analysis

Step 1 — Unadjusted:

If normally distributed	Independent t-test (or Welch's t-test)
If non-normal	Mann-Whitney U test

Step 2 — Adjusted (primary analytical approach):

Multiple linear regression with RMT as dependent variable

Covariates: Treatment group, age, BMI, gestational age, uterine exteriorization, surgeon category, labor duration, CS indication

Reported: Adjusted MD, 95% CI, R^2 , adjusted R^2 , F-statistic, model p-value

Assumption verification: Linearity, homoscedasticity (Breusch-Pagan), independence (Durbin-Watson), multicollinearity ($VIF < 5$), normality of residuals (Shapiro-Wilk)

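### The ΔHb analyses leave out pre-operative hemoglobin as a covariate although it is collected, which costs precision in this secondary comparison

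*SAP*

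**What the plan says.** Protocol section 9.2 defines ΔHb as pre-operative hemoglobin minus "Hb at Day 1 postpartum". Both values are in the section 10 schedule: the pre-operative row has "baseline NFS (CBC), demographics" and the Day 1 row has "NFS (hemoglobin), vital signs, wound assessment". SAP-3 lists "pre-operative hemoglobin and hematocrit" among the baseline variables to be summarized.

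For the comparison between arms, SAP-5.6 gives only "t-test or Mann-Whitney U; mean difference with 95% CI". SAP-5.1 adds a general rule for continuous secondary outcomes: "Adjusted: Multiple linear regression (same covariate set". The set meant is that of the RMT model in SAP-4.2. The SAP inside the combined document (section 6.1) gives the same list: "Covariates: Treatment group, age, BMI, gestational age, uterine exteriorization, surgeon category, labor duration, CS indication". Neither list contains pre-operative hemoglobin or hematocrit.

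The combined document's SAP has no rule specific to ΔHb; its section 7.2 gives Mann-Whitney for intraoperative continuous outcomes. SAP-9 calls secondary outcomes exploratory and applies Holm-Bonferroni to them.

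**The concern.** Subtracting the baseline is the same as adjusting for it with a slope fixed at 1. Unless the two measurements are perfectly correlated (with equal SDs), that slope is too steep: women who start high tend to show larger falls whatever the closure technique. Two things follow. The confidence interval for the treatment difference is wider than it need be. And if the arms happen to differ in pre-operative hemoglobin, part of that difference stays in the ΔHb estimate.

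Blood loss is a stated secondary objective. The visual estimate depends on canister volume less an estimate of amniotic fluid, and the calculated loss depends on a weight-based volume formula. ΔHb needs neither, so an efficient analysis of it is worth having. If Table 1 shows an imbalance and the covariate is added only then, that would be the kind of post-hoc decision that SAP-1 sets out to avoid.

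**Working it through.** **The plan's own figure.** The only sample-size calculation is for RMT at 6 months (protocol section 11): 2 × (1.96 + 0.842)² × 3.5² / 1.3² = 113.8, so 114 per group, as stated. Nothing is sized for ΔHb. The one input taken from section 11 is the 192 women per arm.

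**Assumptions.** The documents give neither a hemoglobin SD nor a correlation ρ between pre-operative and Day 1 values. I assume equal SDs σ at the two times and show a range of ρ. The comparison is with the t-test branch of SAP-5.6; the Mann-Whitney branch is not quantified.

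**Precision.** Per woman, Var(change) = 2σ²(1−ρ), and the ANCOVA residual variance is σ²(1−ρ²). The ratio is (1−ρ²) / [2(1−ρ)] = (1+ρ)/2.

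**Power.** Take an effect that the raw change detects with 80% power at two-sided 0.05, so effect/SE = 1.960 + 0.842 = 2.802. ANCOVA power is Φ(2.802/√((1+ρ)/2) − 1.960). At ρ = 0.5: 2.802/0.866 = 3.235; 3.235 − 1.960 = 1.275; Φ = 90%. The sample size cancels.

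**Chance imbalance.** Given a baseline difference d, the expected Day 1 difference with no treatment effect is ρd, so the change-score estimate shifts by d − ρd = (1−ρ)d. The SE of a baseline difference at 192 per arm is √(2/192) = 0.102 SD. A 1-SE imbalance therefore shifts the estimate by (1−ρ) × 0.102 SD, which is √((1−ρ)/2) of the estimate's own SE.

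| ρ (assumed) | Variance, ANCOVA / raw change | SE ratio | Power if raw change has 80% | Shift at 1-SE imbalance (Hb SD) | Same, in SEs of the estimate |
|---|---|---|---|---|---|
| 0.5 | 0.75 | 0.87 | 90% | 0.051 | 0.50 |
| 0.7 | 0.85 | 0.92 | 86% | 0.031 | 0.39 |
| 0.8 | 0.90 | 0.95 | 84% | 0.020 | 0.32 |
| 0.9 | 0.95 | 0.97 | 82% | 0.010 | 0.22 |

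**Simulation check.** There were 10,000 trials of 192 per arm at each of ρ = 0.5, 0.7 and 0.8, with no treatment effect:

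- The raw-change estimate averaged 0.00 SD, with type I error between 4.7% and 5.3%.
- Simulated variance ratios were 0.764, 0.843 and 0.907, against 0.75, 0.85 and 0.90 from the formula.
- Among trials with a baseline difference above 1 SE in one direction, the raw-change estimate was off by 0.077, 0.049 and 0.028 SD on average. ANCOVA was off by no more than 0.0024 SD.

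**The case against.** The strongest reply is that the planned analysis is valid. With 1:1 randomization the change score is unbiased and holds its type I error, as the simulation shows. A reader might infer that SAP-5.6 biases the ΔHb comparison; that is true only conditionally, once a particular chance imbalance has been observed. This stands. The shift is also modest: if the hemoglobin SD is assumed to be 1.0 to 1.5 g/dL, a 1-SE imbalance moves the estimate by 0.05 to 0.08 g/dL at ρ = 0.5 and 0.02 to 0.03 g/dL at ρ = 0.8.

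A reader might also infer that no covariate adjustment is planned. SAP-5.1 does plan some for continuous secondary outcomes, and nothing in SAP-5.6 excludes ΔHb from it. The gap is one missing covariate, and the table measures the gain over the raw change, not over the SAP-5.1 model. This stands too.

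The power figures rest on an unknown ρ and a constructed 80% starting point. Under Holm-Bonferroni, power at an unadjusted 0.05 is not the operating power of this outcome. They illustrate relative efficiency only, and at ρ = 0.9 the gain is about 2 points.

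Last, the change comes late. Recruitment ended on 31 December 2025 (protocol section 4.3), the SAP is dated April 2026, and the principal investigator holds both clinical and allocation data (sections 7.3 and 13). That is a reason to document and date the change, not to leave the covariate out.

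**Conclusion.** The point holds as a minor, inexpensive gain in precision. Pre-operative hemoglobin is collected, and no planned model for ΔHb uses it. Relative to the raw change, adding it removes 25% of the variance at ρ = 0.5, 15% at 0.7, 10% at 0.8 and 5% at 0.9, and it removes the dependence on chance baseline imbalance. These figures assume equal SDs before and after surgery and a ρ that the documents do not supply.

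The scope is narrow. It would be wrong to extend the point to blood loss as a whole: the visual estimate (PSTEV) uses no hemoglobin, and the calculated loss (PSTC) uses hematocrit and has its own test. ΔHb is secondary and exploratory, so no primary conclusion depends on it.

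**What to change.** In SAP-5.6, before any unblinded analysis, name as the main ΔHb analysis a linear regression of ΔHb on treatment group with pre-operative hemoglobin as a covariate. In practice this adds pre-operative hemoglobin to the SAP-5.1 covariates for this one outcome. Day 1 hemoglobin may be the dependent variable instead; the treatment estimate is the same apart from its sign. Report the adjusted mean difference with its 95% CI, and keep the raw ΔHb per arm as a descriptive figure. Carry the same rule into the combined document's SAP, which has none for ΔHb.

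No new data are needed. The cost is a short SAP amendment, with the change, its reason and its date recorded, because Day 1 data collection was already complete on the stated timeline.
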